6. TREATMENT COMPARISONS

[figure not shown]
The primary comparison of interest is TQ+CQ versus PQ+CQ on the risk of relapse over the six month period post-dosing, with a primary objective of assessing non-inferiority. Superiority of TQ+CQ over PQ+CQ will be claimed if it exists.

The upper 95% confidence bound of the hazard ratio will be compared to a pre-specified non-inferiority margin (further details in Section 9). If the upper bound is:

- Less than one, then TQ+CQ will be declared both non-inferior and superior to PQ+CQ.
- Less than the non-inferiority limit and greater than one, then TQ+CQ will be declared non-inferior to PQ+CQ.
- Either equal to or greater than the non-inferiority limit, then non-inferiority between TQ+CQ and PQ+CQ has not been demonstrated.

Figure 1 shows the graphical interpretations of the possible TQ+CQ versus PQ+CQ hazard ratios and 95% confidence intervals.

Figure 1 Interpretation of the TQ+CQ versus PQ+CQ hazard ratio and 95% confidence interval (M2 represents the pre-determined non-inferiority margin).

For data displays, and throughout this document, treatment groups are defined using the following descriptors:

Treatment Group	Short Label Descriptor
Tafenoquine 300 mg + chloroquine	TQ+CQ
Primaquine + chloroquine	PQ+CQ
Chloroquine	CQ only

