3. DATA SOURCES/STUDIES INCLUDED

- The individual patient data from the PQ+CQ and CQ only arms of the DETECTIVE Part 1 study will be used alongside published data and clinical opinion to define the non-inferiority limit (further details in Section 9.2)
- The individual patient data from the TQ+CQ and PQ+CQ arms of the DETECTIVE Part 2 and GATHER studies will be used to calculate a combined hazard ratio and 95% confidence interval (further details in Section 9.4).

DETECTIVE Part 1

TAF112582 (DETECTIVE) is a seamless phase II/III, multi-centre, double-blind, double-dummy, parallel group, randomised, active control study. In Part 1 (phase 2b) of the study, all subjects were treated with CQ on Days 1 to 3 (600 mg, 600 mg, 300 mg) to treat the blood stage malaria infection. Subjects were randomised to one of six groups (ratio 1:1:1:1:1:1):

- Placebo (CQ only),
- Single dose TQ 50mg,
- Single dose TQ 100mg,
- Single dose TQ 300mg,
- Single dose TQ 600mg, or
- 15mg PQ od for 14 days.

A total of 329 subjects were enrolled in this study. Subjects were followed up for six months to assess the proportion of subjects who remained relapse free in that time.

DETECTIVE Part 2

The Part 2 of TAF112582 is a Phase III confirmatory trial which is currently ongoing and has enrolled 522 subjects. All subjects received open label CQ for the first three days of the study to treat the blood stage of the infection. Subjects were randomised to one of three groups (ratio 2:1:1):

- Single dose TQ 300mg,
- PQ 15 mg od for 14 days, or
- Placebo (CQ only).

The primary endpoint (% relapse-free efficacy over six months) is the same as for Part 1 (phase 2b) of the study.

GATHER

The phase III study TAF116564 (GATHER) is similar in design to pivotal Part 2 of DETECTIVE. It is a prospective, double-blind, multicenter study where a total of 251 subjects have been randomised. All subjects received open label CQ for the first three days of the study to treat the blood stage of the infection. Subjects were randomised to one of two groups (ratio 2:1):

- Single dose TQ 300mg, or
- PQ 15mg od for 14 days.

This study does not contain a placebo arm, as the primary endpoint is safety, and efficacy is a secondary endpoint. However, efficacy assessment methodology and timings, and duration of follow-up are identical to DETECTIVE.

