9. ANALYSES

9.1. The non-inferiority margin

The time to relapse hazard ratio and 95% confidence interval for CQ only versus PQ+CQ in DETECTIVE Part 1 is 3.68 (1.84 to 7.35). This can be considered a comparison of PQ versus placebo given CQ only treats the acute parasitemia, so does not prevent relapse. [Table 1](#) presents a range of preserved effects (preserving the difference versus placebo) based on the lower bound of the 95% confidence interval of 1.84. For example, a preserved effect of 50% would result in a non-inferiority margin of 1.42.

Table 1 Non-inferiority margins for a range of preserved effects.

No preserved effect	50%	66%	75%	80%	100%
1.84	1.42	1.29	1.21	1.17	1.00

The binary relapse/relapse-free data at six months, which contributes to the overall hazard ratio of 1.21, translates to an odds ratio of 1.45 (see Section 9.5).

The combined DETECTIVE Part 2 and GATHER sample size is expected to be 642, with 428 on TQ+CQ and 214 on PQ+CQ. Based on these figures, if the PQ+CQ efficacy is 60.3% then an odds ratio of 1.45 equates to a PQ+CQ minus TQ+CQ efficacy difference of 9.1%. Table 2 shows the PQ+CQ minus TQ+CQ percentage differences for a range of efficacies.

Table 2 PQ+CQ minus TQ+CQ percentage differences for a range of efficacies (based on an odds ratio of 1.45).

PQ efficacy (%)	TQ efficacy (%)	Difference (%)
40.2	31.8	8.4
50.0	40.9	9.1
60.3	51.2	9.1
70.1	61.9	8.2
80.4	73.8	6.5

During discussions with the clinical team on 7th September 2016 a preserved effect of 75% was chosen, resulting in a non-inferiority margin of 1.21. This value is considered not to represent a clinically meaningful difference. Section 9.2 contains details about the statistical reasoning underpinning the selection of the non-inferiority margin.

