9.4. Meta-analysis

Using the individual subject level data from the TQ+CQ and PQ+CQ arms of DETECTIVE Part 2 and GATHER, a Cox proportional hazards model will be fitted with region, study and treatment as covariates. The hazard ratio of TQ+CQ versus PQ+CQ, plus the associated 95% confidence interval and p-value, will be presented. The upper bound of the 95% confidence interval will be compared to the non-inferiority limit of 1.21 and interpreted as outlined in Section 6.

Interactions between study and treatment, and region and treatment will be assessed at the 10% (2-sided) level of significance. If any significant interactions are identified from the Cox proportional hazards model, they may be further investigated by presentation of the time-to-relapse hazard ratios and 95% confidence intervals for each study and/or region separately.

A Kaplan-Meier survival curve with 95% confidence bands and a log-log plot will be produced.

An important assumption underpinning the Cox proportional hazards model is that of proportional hazards. The proportional hazards assumption will therefore be assessed and will include a visual check of the Kaplan-Meier curves. The shape of the curves should be similar for the TQ+CQ and PQ+CQ treatment groups with the separation between the curves remaining proportional across time. A complementary log-log plot will also be used to check the proportional hazards assumption. In this plot both treatment group lines should appear approximately linear.

In the event that the proportional hazards assumption is considered violated the primary comparison will be based on a logistic regression model. The treatment difference will then be assessed for non-inferiority based on the upper bound of the 95% confidence interval surrounding the odds ratio. Further details in Section 9.5.

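### The non-inferiority rule never checks that primaquine worked in the pooled trials, although DETECTIVE Part 2 randomises a CQ-only arm that could show it

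*Supplement*

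**What the plan says.** The Meta-Analysis Plan (207581) sets the decision rule in section 6 and repeats it in section 9.4: "The upper bound of the 95% confidence interval will be compared to the non-inferiority limit of 1.21". An upper bound below 1 gives non-inferiority and superiority. A bound between 1 and the limit gives non-inferiority: "Less than the non-inferiority limit and greater than one, then TQ+CQ will be declared non-inferior to PQ+CQ". No other result enters the rule.

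The limit is built in sections 9.1 and 9.2 from DETECTIVE Part 1, where the CQ-only v PQ+CQ hazard ratio was 3.68 (1.84 to 7.35), with India left out because relapse there was very low. Of that ratio the plan says "This can be considered a comparison of PQ versus placebo given CQ only treats the acute parasitemia, so does not prevent relapse". Starting from the lower bound, "a preserved effect of 75% was chosen, resulting in a non-inferiority margin of 1.21". Section 9.3 then checks Part 1 against two published reviews.

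On the data to be pooled, section 3 says "The individual patient data from the TQ+CQ and PQ+CQ arms of the DETECTIVE Part 2 and GATHER studies will be used". DETECTIVE Part 2 "is a Phase III confirmatory trial which is currently ongoing and has enrolled 522 subjects", allocated 2:1:1 to TQ, PQ and CQ only. GATHER has no CQ-only arm. The display titles in section 11.2 do not name a CQ-only contrast; the shells are in a separate document (section 11.3).

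**The concern.** A margin that preserves part of a comparator's effect means something only if the comparator had that effect in the trials being analysed. Here the effect comes from an earlier trial part, and its plausibility is checked only against literature. A hazard ratio near 1 between TQ and PQ is what would be seen if both drugs worked, and also if neither did. The rule cannot tell these apart.

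At stake is the meaning of the claim. A reader will take non-inferiority with 75% preserved effect to mean that TQ keeps most of PQ's protection. If PQ gave little protection in these trials, that conclusion would be false even though TQ was no worse than PQ. The randomised data that bear on this exist in Part 2, and the plan does not tie the declaration to them.

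**Working it through.** **Inputs (Meta-Analysis Plan)**
- Enrolment: Part 2, 522 at 2:1:1; GATHER, 251 at 2:1 (section 3).
- Part 1 CQ only v PQ+CQ: 3.68 (1.84 to 7.35) (section 9.1).
- Part 1 six-month relapse: 12/40 = 30.0% on PQ+CQ, 30/42 = 71.4% on CQ only (section 9.3).
- Limits: 1.21 for the hazard ratio (section 9.1), 1.45 for the fallback odds ratio (section 9.5).

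**1. Reproducing the plan's figures.** TQ: 522 x 2/4 + 251 x 2/3 = 428.3. PQ: 522/4 + 251/3 = 214.2. This matches "The combined DETECTIVE Part 2 and GATHER sample size is expected to be 642, with 428 on TQ+CQ and 214 on PQ+CQ". Margin: 1 + 0.25 x (1.84 - 1) = 1.21. Odds-ratio margin: 1 + 0.25 x (2.80 - 1) = 1.45. All agree. The CQ-only arm of Part 2 is 522/4, about 130.

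**2. What 1.21 requires.** If the true CQ-only v PQ+CQ hazard ratio in the pooled trials is H, a TQ v PQ ratio of 1.21 preserves 1 - 0.21/(H - 1) of the excess. At H = 1.84 that is 1 - 0.21/0.84 = 75%. At H = 1.21 it is zero. So 75% preservation needs H of at least 1.84, and any preservation needs H above 1.21.

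**3. Chance of declaring non-inferiority at a true TQ v PQ ratio of 1.** The plan gives no power or event count, so events are taken as d = N x relapse rate (an assumption). SE = 1/sqrt(d x 2/3 x 1/3) and P = Phi(ln 1.21/SE - 1.96), with ln 1.21 = 0.1906.

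| Scenario, N = 642 | d | SE | P | Simulated |
|---|---|---|---|---|
| Neither works, 71.4% relapse | 459 | 0.099 | 48.6% | 49.2% |
| Both work, 30% relapse | 193 | 0.153 | 23.8% | 25.1% |

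The simulation used 4,000 trials, exponential times, censoring at 180 days and a Cox model with treatment only. Of the 48.6%, 2.5 points also cross into superiority, leaving 46.1% for the quoted bullet alone.

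**4. Sensitivity.** The primary population is per protocol (section 5) and its size is not stated. Keeping 90/80/70% of 642 gives 44.7/40.6/36.4% when neither works, against 21.9/19.9/18.0% when both work. With all 642 and neither drug working, common relapse rates of 50/60/80% give 36.3/42.2/53.1%.

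**5. Fallback odds-ratio rule.** SE = sqrt[(1/428 + 1/214)/(p(1 - p))] and P = Phi(ln 1.45/SE - 1.96). At p = 0.714, SE = 0.185 and P = 51.8%. At p = 0.30, SE = 0.183 and P = 52.9%.

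**6. Adding a Part 2 condition: the 95% CI for CQ only v PQ+CQ lies above 1.**
- If PQ is inactive, the condition is met in at most 2.5% of trials, so the joint claim is capped there (simulated 0.35%, down from 49.2%).
- If both drugs work at 30% v 71.4%, the simulated chance of a claim stays at 25.05%; power for the condition at 3.68 exceeds 99%.
- If the true ratio is 1.84, PQ relapse consistent with 71.4% on CQ only is 1 - 0.286^(1/1.84) = 49%. With about 130 per arm that gives 64 and 93 events, SE = sqrt(1/64 + 1/93) = 0.162, and power Phi(0.610/0.162 - 1.96), about 96%. At 80% and 70% of the subjects it is about 92% and 88%.

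**The case against.** The strongest reply is that the comparison probably exists elsewhere. The plan's Introduction says the Phase III part of TAF112582 will compare TQ+CQ with CQ only. Part 2's own analysis plan is not shown and may report PQ+CQ v CQ only as well. That stands: what is missing here is a condition or cross-reference in the meta-analysis rule, not necessarily the contrast. The rule as written still declares non-inferiority whatever Part 2 shows.

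Second, the margin is already conservative: it uses the lower confidence bound, preserves 75% of it and is checked against literature. This also stands, but those steps discount uncertainty in the past effect; they do not test whether the effect recurred.

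Third, the scenario with neither drug working at 71% relapse is extreme, and nothing in the documents suggests it is likely. Two causes a reader might offer do not produce it. Few hypnozoites would mean few relapses, and at 5-20% relapse the same formula gives only about 7-17%. Poor adherence to the 14-day course would not disable a single observed TQ dose and would move the ratio in TQ's favour; the GATHER analysis plan also excludes subjects who miss two or more outpatient doses from the per-protocol set.

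Fourth, the proposed condition is partial. With 39 and 93 events (30% v 71%), an observed ratio of about exp(1.96 x 0.191) = 1.45 would pass, so it does not confirm 1.84. It also says nothing directly about GATHER, which supplies about 84 of the 214 PQ subjects. Both limits should be stated.

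**Conclusion.** The concern holds. The declaration rests on an untested assumption that the Part 1 primaquine effect recurred, although a concurrent randomised control in Part 2 could test it in the study that supplies about 61% of the pooled subjects (391.5 of 642.5). On the primary hazard-ratio rule, the chance of a declaration when neither drug works is about twice that when both work: about 49% v 24% with all 642 subjects, 36-45% v 18-22% in a per-protocol set 10-30% smaller. These figures assume a true TQ v PQ ratio of 1 and the Part 1 relapse rates.

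Four stronger readings are not supported:
- That the rule inflates type I error for TQ v PQ. With both drugs inactive the true ratio is 1, so no worse than PQ is literally correct. What fails is the inference of retained benefit.
- That the rule always favours failure. On the fallback odds-ratio rule the two chances are about equal (51.8% v 52.9%), though inactive PQ still goes undetected.
- That the margin is meaningless unless PQ's effect reaches 1.84. That value is needed for 75% preservation; some effect is preserved above 1.21.
- That CQ only is displayed nowhere. The titles do not name it, but section 6 defines a label for it and the shells are not shown.

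**What to change.** In section 6, add that non-inferiority is declared only if the 95% CI for CQ only v PQ+CQ in DETECTIVE Part 2 lies above 1, using the section 9.4 Cox model without the study term and the same population. Use the odds ratio if the section 9.5 fallback applies. Report that ratio beside the Part 1 value (3.68, lower bound 1.84), and report TQ+CQ v CQ only. If the condition fails, give the TQ v PQ estimate and interval without a non-inferiority claim. Add the CQ-only arm of Part 2 to section 3 and the contrasts to section 11.2.

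State in the plan that passing shows some primaquine effect in Part 2, does not establish 1.84, and cannot be checked in GATHER.

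The cost is a short addition to the text and two Cox contrasts on an arm already randomised; the main condition needs only one. The downside is a small loss of power if primaquine's true effect is near 1.84, where the condition itself has power of roughly 88-96%. It should be fixed before database lock, as section 1 requires of all analysis decisions.

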7. GENERAL CONSIDERATIONS FOR DATA ANALYSES

All statistical summaries and analyses will be performed using SAS software version 9.3 on a UNIX or LINUX platform, unless otherwise specified.

No multiple comparisons will be performed in this analysis and so no adjustments for multiplicity are required.

8. DATA HANDLING CONVENTIONS

8.1. Premature Withdrawal and Missing Data

Both premature study withdrawal and missing data are accounted for in the survival analysis by censoring (see Section 8.2).

Subjects censored prior to six months will be excluded from the secondary endpoint i.e. the logistic regression analysis of the binary outcome of relapse. However if the proportional hazards assumption is violated, see Section 9.4, then some of these subjects will be classified as having relapsed in an additional Missing on or after Day 29=Failure sensitivity analysis (see Section 8.2).

8.2. Derived and Transformed Data

The datasets of both the DETECTIVE Part 2 and GATHER studies will contain key variables that have been derived using the definitions specified below.

Baseline

Randomisation may occur at the Day 1 visit or the Day 2 visit. The last assessment performed prior to the first dose of study medication (CQ or randomised treatment) will be considered baseline.

Six month time to relapse

Relapse is defined by a positive blood smear with or without *P. vivax* symptoms.

- A subject will be considered not to have relapsed at six months for the purposes of the analysis if **all** of the following are true (also described in [Figure 2](#)):
 - Subject had a non-zero *P. vivax* asexual parasite count at baseline. Subjects with no asexual *P. vivax* parasites at this time point will be censored with time to relapse = 0 days.
 - Subject demonstrated initial clearance of *P. vivax* parasitaemia. This is defined as two negative asexual *P. vivax* parasite counts, with at least six hours between the counts, and no positive counts in the interval. Subjects who do not meet this criteria will be classified as relapses, with time to relapse = 0 days.
 - Subject has no positive asexual *P. vivax* parasite count at any assessment prior to or on Study Day 201 following initial parasite clearance. Subjects who do have a positive count will be classified as relapses, with time to relapse = (date of first positive count) – (date of Study Day 1) days.
 - Subject did not take a concomitant medication with anti-malarial activity at any point between Study Day 1 and their last parasite assessment. A list of all concomitant medications will be reviewed by a GSK clinician prior to unblinding

[figure not shown]
the study, and classified accordingly. Subjects who did take a drug with anti-malarial activity but never had a positive asexual *P. vivax* parasite count after initial clearance will be censored, with time to relapse censored at (date of last negative parasite assessment prior to concomitant medication start) – (date of Study Day 1). If a subject has not had a negative assessment prior to the concomitant medication start date, they will be censored at 0.

- Subject is parasite-free at six months. This is defined as a negative asexual *P. vivax* parasite count at the first parasite assessment performed on or after Study Day 166.
- Subjects who do not have a positive asexual *P. vivax* parasite count following initial clearance but where the final parasite count occurred before Study Day 166 will not have been classified by the preceding rules. These subjects will be considered to be censored, with time to relapse censored at (date of final parasite assessment) – (date of Study Day 1).

If a subject has a relapse outcome and a censored outcome, they will be considered to be a relapse, even if the time point of the relapse is later than the time point of censoring. For example, a subject who took a medication with anti-malarial activity at Study Day 32, but remained parasite-free after initial clearance until Study Day 68 will be treated as a relapse at Study Day 68.

Flow chart of algorithm:

Figure 2 Flowchart of algorithm for six month time to relapse

**Missing on or after Day 29=Failure definition**

In the event that the proportional hazards assumption is violated (see Section 9.4), resulting in the odds ratio being assessed for non-inferiority (see Section 9.5), then the following Missing on or after Day 29=Failure definition will be used in an additional sensitivity analysis.

- In addition to those with a positive asexual *P. vivax* parasite count at any assessment prior to or on Study Day 201, the following subjects will also be defined to have relapsed:
 - Subject did not demonstrate initial clearance of *P. vivax* parasitaemia (i.e. did not have two negative asexual *P. vivax* parasite counts, with at least six hours between the counts, and no positive counts in the interval)
 - Subject took a concomitant medication with anti-malarial activity at any point between Study Day 1 and their last parasite assessment. A list of all concomitant medications will be reviewed by a GSK clinician prior to unblinding the study, and classified accordingly.

- Subject with a missing parasite assessment on or after Study Day 29.
- Subjects with a zero *P. vivax* asexual parasite count at baseline will be excluded from the analysis.

All data summaries of the mITT population will be performed with no replacement of missing electronic case report form (eCRF) efficacy and safety data.

Exposure and Treatment Compliance

For the first three days of the study, all study medication will be administered in the presence of the Investigator or study nurse, and ingestion confirmed.

On any day of in-clinic dosing, a subject will be classified as compliant with daily administered dose if they do not vomit the initial dose or if they are successfully re-dosed. A subject is considered to be compliant in clinic if they retain all study medication given to them on all three days of dosing.

Subjects will also take PQ or PQ placebo outside of the clinic to a total of 14 days of PQ/PQ placebo dosing, where administration is not directly observed. Compliance for this study medication will be summarised using the final pill count and PQ PK data.

Compliance determined using Day 8, Day 15, Day 8 or Day 15, Day 8 and Day 15 carboxyPQ PK samples will also be captured.

8.3. Assessment Windows

The following assessment windows were used in both DETECTIVE Part 2 and GATHER.

Visit	Analysis Window	
	Beginning Timepoint	Ending Timepoint
Day 1	Study Day 1	Study Day 1
Day 2	Study Day 2	Study Day 2
Day 3	Study Day 3	Study Day 4
Day 29	Study Day 26	Study Day 32
Day 180	Study Day 166	Study Day 201

Unscheduled and withdrawal visit data will be slotted into a scheduled visit window, if no competing visit exists within the window. If there are multiple assessments within the same window which are not unscheduled visits, the earliest result will be used in the summaries.

Study Day 180 refers to a time point exactly 179 days after Study Day 1 (when the first dose of study medication including CQ was taken), whereas the ‘Day 180 visit’ refers to the nominal Day 180 assessments which did not necessarily occur on Study Day 180.

8.4. Subgroup and Covariate Definitions

Both study and region will be included as covariates. The randomisation was not stratified for both DETECTIVE Part 2 and GATHER, so no additional covariate adjustment is required.

Breakdown of countries within each study

Countries	DETECTIVE Part 2	GATHER
Brazil	x	x
Peru	x	x
Thailand	x	x
Philippines	x	
Ethiopia	x	
Cambodia	x	
Colombia		x
Vietnam		x

Regions are defined geographically for inclusion as a covariate as:

Region	Countries
South America	Brazil, Peru, Colombia
Asia	Thailand, Vietnam, Cambodia, Philippines
Africa	Ethiopia

